11.6.2.4 Conjunctival Redness Score Assessment

The Efron scale/conjunctival redness assessment ([Efron et al. 2001](#)) is a clinically validated, image-based scale that will be used to evaluate bulbar conjunctival redness during all ophthalmologic examinations, as outlined in [Table 1](#) (all cohorts) and specified in [Table 2](#), [Table 3](#), [Table 4](#), and [Table 5](#) for Cohorts A, B, C, and D, respectively. The scale contains 5 categories ranging from 0 (normal) to 4 (severe).

For each treatment period, the baseline assessments are measured on Day -2 and -1 at predose/morning, +1, +3, +6, and +12 hours. Baseline conjunctival redness score is defined as

the single assessment at Day -1. A separate baseline will be derived for each scheduled time point. Change from baseline will be calculated comparing post treatment values to their respective baseline (e.g., on treatment predose assessments will be compared to baseline predose assessments, on treatment 1 hours assessments will be compared to baseline 1 hour assessments, on treatment 3 hours assessments will be compared to baseline 3 hour assessments, on treatment 6 hours assessments will be compared to baseline 6 hour assessments and on treatment 12 hours assessments will be compared to baseline 12 hour assessments).

The number and percentage of subjects in each score category at each time point will be summarized by eye (study eye, non-study eye, and either eye (MDTP only)), and treatment. For either eye assessments, the eye with the greater score will be summarized. The denominator of the percentage is the number of subjects who have the assessment for the specified eye and visit. In addition, the number and percentage of subjects with clinically significant results, and non-clinically significant results will be summarized by treatment group. Results of conjunctival redness score assessment will be listed by individual subject.

Additionally, the number and percentage of subjects with conjunctival redness score changes from baseline in the following categories by eye (study eye, non-study eye, and either eye (MDTP only)) and treatment group will be presented:

- -4 (4 points decreased from baseline)
- -3 (3 points decreased from baseline)
- -2 (2 points decreased from baseline)
- -1 (1 point decreased from baseline)
- 0 (no change from baseline)
- 1 (1 point increased from baseline)
- 2 (2 point increased from baseline)
- 3 (3 point increased from baseline)
- 4 (4 point increased from baseline)

The percentages will be calculated relative to the number of subjects with available baseline conjunctival redness score and at the postbaseline assessment for the given timepoint. For either eye summaries, at baseline, the eye with the higher baseline redness score will be summarized. For post baseline timepoints, the eye with the smaller decrease from baseline will be summarized. If both eyes have the same change from baseline, the eye with the higher redness score at the given visit will be summarized.

11.6.2.5 Corneal Haze

Corneal haze assessments will be performed as part of the slit lamp examination at the time points outlined in [Table 1](#) (all cohorts) and specified in [Table 2](#), [Table 3](#), [Table 4](#), and [Table 5](#) for Cohorts A, B, C, and D, respectively.

The number and percentage of subjects for each category of corneal haze grade will be summarized by eye (study eye, non-study eye, and either eye (MDTP only)) and treatment group at each visit and time point. For either eye assessments, the eye with the greater score

will be summarized. The denominator of the percentage is the number of subjects who have the assessment for the specified eye and visit. In addition, the number and percentage of subjects with clinically significant results, and non-clinically significant results will be summarized by treatment group. Results of corneal haze assessment including corneal haze grade, epithelial edema, stromal thickening/haze, and Descemet's folds will be listed by individual subject and a separate listing of clinically significant findings will also be presented.

11.6.2.6 Corneal Epithelial Integrity by Fluorescein Stain

The integrity of the corneal epithelium will be assessed using topically applied fluorescein at the time points outlined in [Table 1](#) (all cohorts) and specified in [Table 2](#), [Table 3](#), [Table 4](#), and [Table 5](#) for Cohorts A, B, C, and D, respectively. It is important to perform the assessment before instillation of topical anesthetic for measurement of IOP.

For each subject at each visit and timepoint, a total score of three components from corneal epithelium integrity will be calculated by adding scores across three regions: inferior, central, and superior for each eye. The total scores will be summarized. For each treatment period, the baseline assessments are measured on Day -2 and -1 at predose/morning, +2, +4, +8, and +12 hours. Baseline corneal epithelial integrity is defined as the single assessment at Day -1 at each scheduled time point. Change from baseline will be calculated comparing post treatment values to their respective baseline (e.g., on treatment predose assessments will be compared to baseline predose assessments, on treatment 2 hours assessments will be compared to baseline 2 hour assessments, on treatment 4 hours assessments will be compared to baseline 4 hour assessments, on treatment 8 hours assessments will be compared to baseline 8 hour assessments and on treatment 12 hours assessments will be compared to baseline 12 hour assessments).

Descriptive statistics for corneal epithelial integrity total scores and change from baseline at each assessment time point will be presented by eye (study eye, non-study eye, and either eye (MDTP only)) and treatment group. For either eye summaries, at baseline the eye with the greater staining total score will be summarized. For post baseline timepoints, the eye with the greater increase from baseline will be summarized. If both eyes have the same change from baseline, the eye with the greater staining total score at the given visit will be summarized. In addition, the number and percentage of subjects with clinically significant results, and non-clinically significant results will be summarized by treatment group. Results of corneal epithelium integrity assessment including individual region scores will be listed by individual subject and clinically significant findings will also be presented.

11.6.2.7 Anterior Chamber Cell and Flare

Anterior chamber cell and flare will be assessed and graded using the Standardization of Uveitis Nomenclature grading scale at the time points outlined in [Table 1](#) (all cohorts) and specified in [Table 2](#), [Table 3](#), [Table 4](#), and [Table 5](#) for Cohorts A, B, C, and D, respectively.

The number and percentage of subjects for each anterior chamber cells grade and anterior chamber flare grade will be summarized by eye (study eye, non-study eye, and either eye (MDTP only)) and treatment group. For either eye summaries, the eye with the greater score will be

summarized. The denominator of the percentage is the number of subjects who have the assessment at the specified eye and visit. In addition, the number and percentage of subjects with clinically significant results, and non-clinically significant results will be summarized by treatment group. Results of anterior chamber cell and flare assessment will be listed by individual subject and clinically significant findings will also be presented.

11.6.2.8 Lens Opacification

Lens opacification will be assessed with the slit lamp during dilated examination. Phakic eyes will be graded in the nuclear, cortical, and posterior subcapsular layers using the Lens Opacities Classification System III grading scale at the time points outlined in [Table 1](#) (all cohorts) and specified in [Table 2](#), [Table 3](#), [Table 4](#), and [Table 5](#) for Cohorts A, B, C, and D, respectively. Pseudophakic eyes without posterior capsulotomy will be graded in the posterior subcapsular layer only. Pseudophakic eyes with posterior capsulotomy will not be graded.

The number and percentage of subjects that are phakic, the number and percentage of subjects that are pseudophakic, including number and percentage of subjects with and without a posterior capsulotomy, and the number and percentage of subjects for each category of nuclear color/opalescence, cortical, and posterior subcapsular will be summarized by eye (study eye and non-study eye) and treatment group at each visit and time point. The denominator of the percentage is the number of subjects who have the assessment for the specified eye and visit. In addition, the number and percentage of subjects with clinically significant results, and non-clinically significant results will be summarized by treatment group. Results of lens opacification will be listed by individual subject and clinically significant findings will also be presented.

11.6.2.9 Intraocular Pressure

Intraocular pressure will be measured at the following visits:

- Screening
- Midwashout assessment
- SDTP (Cohort A only): baseline (Days -2 and -1), Days 1 and 2
- MDTP (all cohorts): baseline (Days -2 and -1) and Days 1, 2, 7, 14, 21, 27, 28, and 29.

See [Table 2](#), [Table 3](#), [Table 4](#), and [Table 5](#) for detailed timings by cohort. Two consecutive IOP measurements, to the nearest mmHg, will be made in the designated study eye; if the 2 measurements differ by more than 2 mmHg, then a third measurement will be performed. The procedure will be repeated in the nonstudy eye. All measurements will be recorded in the source document and eCRF and the mean of the (2 or 3) readings for each eye will be used to determine the mean IOP at the given time point for each eye. These mean IOP values will be used for all IOP analyses.

The baseline IOP is defined as the average of the mean IOP measurements at Day -1 and Day -2. A separate baseline will be derived for each scheduled timepoint. Descriptive statistics for IOP, the change from baseline, and the percentage change from baseline at each assessment time point

will be presented by eye (study eye vs. non-study eye) and treatment. Change from baseline will be calculated comparing post-treatment values to their respective baselines (e.g., on treatment pre-dose assessments will be compared to baseline pre-dose assessments, on treatment 1 hour assessments will be compared to baseline 1 hour assessments and on treatment 12 hour assessments will be compared to baseline 12 hour assessments). Line plots displaying mean IOP, change from baseline, and percent change from baseline at each visit and each scheduled timepoint will be presented by eye (study eye, non-study eye) and treatment for SDTP and MDTP. Line plots displaying mean IOP, at selected visits (baseline, Day 14 and Day 28) and selected scheduled timepoints (predose, +2h, +4h, +8h) during MDTP will be presented for study eye by treatment. Spaghetti plots showing the IOP values at each visit and each timepoint for all subjects in the Safety set will be presented by eye (study eye, non-study eye) and treatment for SDTP and MDTP.

Diurnal fluctuation in IOP will be summarized as below:

- The baseline diurnal IOP (schedule 1) is defined as the average of all IOP measurements across three time points (predose, +2 h, +8 h) at Day -1 and Day -2. Postbaseline diurnal IOP is defined as the average of all IOP measurements across three time points (predose, +2 h, +8h) at each visit. Change from baseline will be calculated as the difference between postbaseline diurnal IOP and baseline diurnal IOP. Descriptive statistics for diurnal IOP, the change from baseline, and the percentage change from baseline at each visit will be presented by eye (study eye, non-study eye) and treatment.
- The baseline diurnal IOP (schedule 2) is defined as the average of all IOP measurements across three time points (predose, +4 h, +8 h) at Day -1 and Day -2. Postbaseline diurnal IOP is defined as the average of all IOP measurements across three time points (predose, +4 h, +8h) at each visit. Change from baseline will be calculated as the difference between postbaseline diurnal IOP and baseline diurnal IOP. Descriptive statistics for diurnal IOP, the change from baseline, and the percentage change from baseline at each visit will be presented by eye (study eye, non-study eye) and treatment.

Results of intraocular pressure will be listed by individual subject.

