6.2.3 Dosing

6.2.3.1 Dosing Procedures

After satisfying all screening and entry criteria for the study before dosing on Day 1 of each cohort, subjects will be randomized to receive either SHP639 ophthalmic solution or placebo, respectively. Investigational product (SHP639 ophthalmic solution or placebo) will be administered topically in 1 designated eye (Cohort A, SDTP only) or in both eyes (Cohort A, MDTP only, and Cohorts B, C, and D) at the time points specified in [Table 1](#).

Subjects will receive their assigned dose as dispensed by the pharmacist or designee at each site. Investigational product will be administered by the principal ophthalmologist or trained designee at each site while subjects are on site, and will then be self-administered by each subject for the remainder of the treatment period.

Subjects should receive the single dose or first dose if multiple daily dosing (depending on cohort assignment) each day between 7:00am and 9:00am. This is particularly important for cohorts C and D as these subjects will receive 3 and 4 doses daily.

In Cohort A only, there will be a SDTP and an MDTP. The 2 treatment periods will be separated by a washout period of 3-14 days. In Cohort A, single-dose administration of the corresponding dose level (concentration) will occur first, followed by the multiple-dose administration of the same dose level (concentration) QD. The dosing regimens for Cohorts B, C, and D will consist of multiple-dose administration of the appropriate dose level concentration BID, TID, or QID, respectively. For all cohorts, the final dose during the MDTP will be administered on the morning of Day 28.

In Cohort A only, as a safety measure, the first 3 subjects in the SDTP will be dosed with a minimum of 1-hour intervals between subjects. Subjects will then be observed overnight and until the next day (24 hours after dosing) with an ophthalmologist on call. If no AEs occur that are consistent with the predefined stopping criteria, dosing the rest of the cohort (Cohort A, single dose) will proceed as previously outlined. Designated study eye criteria are detailed in Section 3.1.1.

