^a Subjects in all cohorts are to be washed out of current medications for up to 28 days, as specified in Protocol Section 5.2.2. The washout may start from Day -28 onwards, depending on

the length of washout required. A MWOA will be performed on both eyes either 14±2 days after a subject starts the washout period or 14±2 days after a previous MWOA.

Subjects will continue not to take prohibited medications until discharge from the site on Day 29 of the MDTP.

^b The SDTP will occur in Cohort A only. Subjects in Cohort A will be admitted to the unit on Day -3 (optional early check-in to unit if more convenient for the subject) or Day -2 before the morning assessments and will be discharged on Day 2 after completion of the evening assessments. All subjects must have checked in to the unit before the ophthalmologic assessments on Day -2.

^c For Cohort A only, there will be a washout period of 3-14 days between the SDTP and the MDTP.

^d For the MDTP, subjects in Cohorts A, B, C, and D will arrive at the unit before the morning assessments and depart after the evening assessments on Days -2 and -1. They will be admitted to the unit on the morning of Day 1 and discharged from the unit after completing the Day 2 assessments. They will arrive at the unit before the morning assessments and depart after the evening assessments on Days 7, 14, and 21. They will be admitted to the unit on the evening of Day 26 and discharged from the unit after completing the assessments on the morning of Day 29. While admitted to the unit, subjects must remain within the unit unless otherwise specified.

^e The final dose will be at approximately 8:00 AM on Day 28.

[30 AUG 2018]

^f Subjects who are prematurely discontinued from the study will complete the Day 29/ET assessments as fully as possible.

^g A follow-up telephone call will take place 7±2 days post discharge from the clinic (Day 29 of MDTP).

^h All eligibility criteria except IOP-related criteria (inclusion criterion 4 and exclusion criterion 4) will be assessed at screening.

ⁱ Excluding Cohort A (previously performed during the SDTP baseline).

^j Breathalyzer test for alcohol and urine screening for drugs of abuse.

^k These assessments will be performed at initial screening and may also be performed at any visit during the screening period.

^l Vital signs include blood pressure, pulse rate, and temperature.

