^m Drop comfort assessments will be performed immediately and 1, 2, and 3 minutes after instillation of the investigational product; to be assessed at morning doses only. If the score is not ≤ 3 at minute 3, the drop comfort assessment should be repeated at minutes 5, 10, and 15 until the score is ≤ 3 . If the score is >3 at minute 15, it should be recorded as an adverse event.

ⁿ If BCVA decreases by 6 or more letters, then a dilated posterior segment examination should be performed.

^o Manifest refraction should be repeated if the BCVA in either eye decreases by 10 or more letters.

^p Conjunctival redness will be evaluated using the Efron scale.

^q SDTP dosing (Cohort A only): investigational product (SHP639 ophthalmic solution or placebo) will be administered once on the morning of Day 1. MDTP dosing: Cohort A=once daily, Cohort B=twice daily, Cohort C=3 times daily, Cohort D=4 times daily; the final dose will be administered on the morning of Day 28. Dose administration will occur during waking hours.

^r The Day 88 visit is 60 days post last dose (Day 28 of MDTP).

^s For Screening, MWOA, and Day 29 visits only one round of ophthalmic assessments needs to be done in the morning.

^t At check-in for overnight stays the following assessments will be performed: physical exam, drugs of abuse screening, alcohol breathalyzer, vital signs, hematology, chemistry, urinalysis, and a single ECG.

^u The Day 88/FU visit is labeled "Day 88" based on a subject's duration of participation from Day 1 (1st dose) of the MDTP. Subjects in cohort A1, A2, and A3 will have been in the study for a longer duration due to the SDTP.

^v At screening IOP may be done at any time during the day. At MWOA (D-14), IOP should be done at 10:00am +3 hours. IOP only needs to be done at one time during screening, MWOA, and Day 29.

Table 2 Detailed Schedule of Events – Cohort A

Assessment	Days Performed (Screening-D29) ^f	Predose/ Morning ^a	0 m	30 m	1 h	2 h	3 h	4 h	6 h	8 h	12 h
		Gonioscopy ^c	SCR, D29.	X							
Specular microscopy, noncontact	SCR. SDTP: D-1, D2. MDTP: D-1, D14, D29.	X									
Corneal pachymetry	SCR. SDTP: D-1, D1, D2. MDTP: D-1, D1, D2, D7, D14, D29.	X			X	X		X			X
Antidrug Ab blood sampling	D-2, D14, D29, D88/FU	X									
Drugs of abuse	SCR, D-14, SDTP: D-2, MDTP: D-2 and D-1, D1, D14, D21, D26.	X									
Alcohol breath test	SCR (D-42), SCR (D-14). SDTP: BL (D-2), MDTP: BL (D-2 and D-1), D1, D14, D21, D26.	X									

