9.2 Measurement of Treatment Compliance

Treatment compliance will be calculated for MDTP only and will be calculated as:

Compliance (%) = (total actual dose administered / total expected dose) × 100;

Where,

1. If the subject completed the treatment: total expected dose = $x \times 27 + 1$ (the last dose was taken on the morning of Day 28)
2. If the subject discontinued the treatment, the date of treatment discontinuation will be used for date of expected last dose and total expected dose will be calculated as: total expected dose = $x \times (\text{date of expected last dose} - \text{date of first dose} + 1)$

Total actual dose = number of total doses taken between scheduled clinic visits + number of total drug instillations during all clinic visits,

Number of total doses taken between scheduled clinic visits is calculated as the

Sum of [$x \times (\text{the date of last dose prior to check-in at the current visit} - \text{date of last drug instillation from previous visit}) - \text{number of missed doses}$]

where $x = 1$ for Cohort A1, A2, and A3

$x = 2$ for Cohort B1, B2, and B3

$x = 3$ for Cohort C1, C2, and C3

$x = 4$ for Cohort D1, D2, and D3

Number of total drug instillations during all clinic visits is the sum of the numbers of drug instillation in all Study Drug Instillation CRFs of a subject.

The latest date of last dose prior to check in is the date found in Study Drug Accountability CRFs of a subject at each scheduled visit. If a subject has terminated the study early, the date of early termination on the Study Completion 1 CRF will be used. Number of missed doses is the numbers of missed doses in Study Drug Accountability CRFs of a subject at each visit. Descriptive statistics for investigational product compliance during the MDTP will be presented by treatment group for the Safety set. Individual subject compliance information will be listed with treatment group indicated.

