12.4 Pharmacodynamic Methods

All the PD analyses will be performed using the Pharmacodynamic set. Intraocular pressure (IOP; mmHg), a PD biomarker, will be measured using Goldmann applanation tonometry.

Intraocular pressure will be measured according to the following schedule:

SDTP (Cohort A only): baseline (Days -2 and -1), Days 1 and 2, at Predose, 0.5, 1, 2, 3, 4, 6, 8, and 12 h

MDTP (Cohort A only): (all cohorts): baseline (Days -2 and -1), Days 1, 2, 27, and 28, at Predose, 0.5, 1, 2, 3, 4, 6, 8, and 12 h

MDTP (all cohorts): Days 7, 14, and 21 at Predose, 2, 4, 8, and 12 h

The individual and mean absolute IOP, IOP reduction from baseline and percentage of IOP reduction from baseline versus time profiles will be presented in figures. Mean plots will be presented using nominal time and individual plots will be presented using actual time.

In addition, the relationship of percentage of IOP reduction from baseline and dose of SHP639 will be presented in a Box-and-Whiskers plot.

Percentage of IOP reduction from baseline measurements data versus time will be used to estimate the PD parameters using Phoenix® WinNonlin® version 6.4 (Certara USA, Inc., Princeton, NJ) for each individual in each treatment by eye (study eye and non-study eye). Baseline is defined as the arithmetic mean of the time-matched IOP measurements on Days -2

and -1 for that particular subject. Potential effect of diurnal change on variation in IOP is accounted for by factoring time-matched baseline in the calculations of percent of IOP reduction from baseline measurements.

Parameter	Definition
IOP reduction from baseline	IOP reduction from baseline is calculated as follows: $\frac{\text{Baseline IOP} - \text{IOP after treatment}}{\text{Baseline IOP}}$
% of IOP reduction from Baseline	Percentage of IOP reduction from baseline is calculated as follows: $\frac{(\text{Baseline IOP} - \text{IOP after treatment})}{\text{Baseline IOP}} \times 100$
E _{max}	Maximum percent IOP reduction from baseline
TE _{max}	Time of E _{max}
AUEC _{0-t}	Area under the effect curve for the percentage of IOP reduction from baseline versus time profile from time zero (predose) to the time of the last measurable percentage of IOP reduction from baseline, calculated using the linear up/log down interpolation rule.
AUEC _{0-τ}	Area under the effect curve for the percentage of IOP reduction from baseline versus time profile over a dosing interval, calculated using the linear up/log down interpolation rule.

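### The selected-visit IOP plot uses Day 28, a one-dose day for BID, TID and QID, beside full-regimen Day 14; Day 27 would be like for like

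*SAP*

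**What the plan says.** **Dosing.** The SAP schedule (2.2, Table 1 footnotes) gives "MDTP dosing: Cohort A=once daily, Cohort B=twice daily, Cohort C=3 times daily, Cohort D=4 times daily". Protocol 6.2.3.1 states: "For all cohorts, the final dose during the MDTP will be administered on the morning of Day 28". The SAP schedule adds a clock time: "The final dose will be at approximately 8:00 AM on Day 28". The compliance formula in SAP 9.2 sets expected doses for a completer at x × 27 + 1 because "the last dose was taken on the morning of Day 28".

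**IOP outputs in SAP 11.6.2.9.**
- The selected-visit plot: "Line plots displaying mean IOP, at selected visits (baseline, Day 14 and Day 28) and selected scheduled timepoints (predose, +2h, +4h, +8h". By its title this is Figure 14.3.7.9.19, which Section 16 flags for the interim.
- Plots covering everything: "Line plots displaying mean IOP, change from baseline, and percent change from baseline at each visit and each scheduled timepoint will be presented by eye".
- Two diurnal means. Schedule 2 reads: "Postbaseline diurnal IOP is defined as the average of all IOP measurements across three time points (predose, +4 h, +8h) at each visit". Schedule 1 uses +2 h in place of +4 h.

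**IOP sampling.** SAP 12.4 places the full within-day profile on "Days 1, 2, 27, and 28, at Predose, 0.5, 1, 2, 3, 4, 6, 8, and 12 h". The label on that line names both Cohort A only and all cohorts. I read it as all cohorts, because Protocol 7.2.2.3 lists IOP on Days 27 and 28 for all cohorts.

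The readable text of SAP 11.6.2.9, 12.4 and 12.5 does not note that Day 28 is a reduced-dose day for Cohorts B-D. SAP 15.8 does not list it among the non-dosing days.

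**The concern.** The secondary objective is to evaluate IOP reduction under different dosing regimens. More frequent dosing should separate from once-daily dosing mainly later in the day, which is when Day 28 withholds the extra doses. In the selected-visit figure, Day 28 is the only end-of-treatment visit and sits next to Day 14, a full-regimen day. A higher +8 h pressure on Day 28 than on Day 14 in a QID cohort could be read as waning effect when it reflects doses not given.

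Day 27 has full dosing and the same IOP time points. It is also the end-of-treatment day for PK in SAP 12.2.1, 12.2.3 and 12.3 (sampling, accumulation, dose proportionality). The figure departs from that practice without a stated reason.

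**Working it through.** **1. Reproduce the SAP's dose count.** With x doses on each of Days 1-27 and one on Day 28, expected doses are x × 27 + 1. Full dosing through Day 28 would be x × 28.

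| Cohort | x | x × 27 + 1 | x × 28 | Given on Day 28 | Omitted on Day 28 |
|---|---|---|---|---|---|
| A (QD) | 1 | 28 | 28 | 1 | 0 |
| B (BID) | 2 | 55 | 56 | 1 | 1 |
| C (TID) | 3 | 82 | 84 | 1 | 2 |
| D (QID) | 4 | 109 | 112 | 1 | 3 |

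The formula agrees with the dosing text. On Day 27 no dose is omitted in any cohort.

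**2. Which Day 28 readings follow an omitted dose.** The dose interval τ is an assumption: the documents say only that dosing is in waking hours and that the first dose falls between 7:00 and 9:00 am. Omitted doses would have fallen at τ, 2τ, … up to (x − 1)τ after the morning dose. A reading is off-regimen if at least one of those times precedes it. A reading due at the same time as a dose is taken as before it.

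| Regimen | τ | Affected among predose, +2, +4, +8 h | 12 h affected? |
|---|---|---|---|
| BID | 3 h | +4, +8 | yes |
| BID | 4-7 h | +8 | yes |
| BID | 8-10 h | none | yes |
| BID | 12 h | none | no |
| TID | 3 h | +4, +8 | yes |
| TID | 4-7 h | +8 | yes |
| TID | 8 h | none | yes |
| QID | 3 h | +4, +8 | yes |
| QID | 4-5 h | +8 | yes |

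Predose and +2 h are never affected at τ of 3 h or more. Day 28 predose follows a complete Day 27.

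**3. Plausible spacing.** If doses are spread evenly over an assumed waking span of 12-16 h, τ = span/(x − 1). QID gives 12/3 = 4 h to 16/3 ≈ 5.3 h. TID gives 12/2 = 6 h to 16/2 = 8 h. BID gives 12 h or more. On that basis QID is affected at +8 h throughout the range, TID at +8 h in all but the 8 h case, and BID at none of the plotted times.

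**4. Weight in each output.**
- Selected-visit figure: Day 28 is 1 of 2 post-baseline visits. For QID at 4-5 h, 1 of its 4 points is off-regimen.
- Diurnal means: the three-point mean can be formed on Days 1, 2, 7, 14, 21, 27 and 28 (Day 29 has one IOP reading). Day 28 is 1 of 7 visits (14%). For QID at 4-5 h, one of its three readings is off-regimen, so a shift of d mmHg at +8 h moves the Day 28 mean by d/3.
- By-time-point and AUEC outputs: these also use the 12 h reading, which is off-regimen for TID and QID, and for BID if τ is under 12 h.

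**The case against.** The strongest reply is that Day 27 is already reported. The plots of mean IOP, change and percentage change cover every visit and time point (Figures 14.3.7.9.16-18). The diurnal tables are by visit, and SAP 12.5 summarises the PD parameters by study day. The MDTP line plots and IOP tables in 11.6.2.9 carry the same interim flag as Figure 14.3.7.9.19, so anyone who suspects waning can check Days 21 and 27. The SAP does not rank the selected-visit figure above the others. All of this stands, and it limits the point to one figure and to labelling.

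A reader might infer more, in three ways that the documents do not support:
- *That the diurnal summaries rest on Day 28.* They are defined for each visit, and Day 27 has its own row.
- *That BID, TID and QID are all measured off-regimen, by 50%, 67% and 75%.* Those are the shares of the day's doses omitted (1/2, 2/3, 3/4), not shares of readings affected. Readings before the second scheduled dose are still on-regimen, and BID is untouched at the plotted and diurnal times when τ is 8 h or more.
- *That the interim dose judgement is compromised.* Protocol 9.5 ties that judgement to Cohorts A1-B3, and the June 2018 interim in SAP 13 was the repeat of B3. These are QD and BID cohorts, for which the figure is little affected. TID and QID enter only through later optional unmasking or the final analysis.

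The objection does not supply a reason for choosing Day 28 over Day 27 in the one figure that selects days.

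**Conclusion.** The point holds in a narrow form. That Day 28 is a one-dose day for Cohorts B-D is certain from the documents, and so is the mismatch with Day 14 in Figure 14.3.7.9.19. Which readings are affected rests on assumed dose intervals: mainly +8 h for QID at about 4-5 h, +8 h for TID only under 8 h, and the 12 h reading in other outputs. The dosing rows of the detailed schedules are not readable here, so this uncertainty is not a fault of the plan.

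The size in mmHg cannot be given, since it depends on how fast the effect wears off. The analyses are descriptive, and no test, error rate or sample size changes. Severity is minor and limited to reporting.

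**What to change.** 1. In SAP 11.6.2.9 and Figure 14.3.7.9.19, replace Day 28 with Day 27 (baseline, Day 14, Day 27), or show both days with Day 28 marked as a one-dose day for Cohorts B-D.
2. State that Day 27 is the end-of-treatment day for IOP comparisons between regimens, in line with the PK analyses.
3. Label Day 28 post-dose values in the diurnal and PD outputs as *after last dose*, so that they are read as a separate profile.

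The cost is SAP and table-shell wording. Day 27 IOP is already scheduled at every time point needed, so no new data are collected. The one downside is that the last on-regimen profile is a day earlier.
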